## **6. STUDY INTERVENTIONS**

### **6.1. Informed Consent**

The subject's signed and dated ICF must be obtained before conducting any study procedures and prior to starting intervention or administering study intervention. See Section 8.1.1.1.

### **6.2. Treatment Period**

ONCT-534 will be self-administered daily throughout the Treatment Period, with clinical and laboratory assessments to be performed as shown in the Schedule of Assessments (Table 1). On certain days indicated on the Schedule of Assessments, the subject will not take their daily dose at home, and ONCT-534 will be administered in the clinic so that blood samples for ONCT-534 PK analysis can be obtained.

The Treatment Period will continue for a total of approximately 2 years (108 weeks). An EOT Visit will be performed after approximately 2 years of treatment, or if the subject stops treatment prior to Week 108.

#### **6.2.1. Administration of ONCT-534**

At their study visits, subjects will be provided with the appropriate number of ONCT-534 tablets of 40 mg strength, 200 mg strength, or both as needed. The 40 mg scored tablet may be broken into two 20 mg halves and the 200 mg scored tablet may be broken into two 100 mg halves. Subjects should bring any empty bottles or unused ONCT-534 pills with them at each visit.

ONCT-534 should be taken by mouth with a small amount of water at the same time each day, at least 2 hours after eating and at least one hour before eating.

Note: On certain clinic visits, as indicated in the Schedule of Assessments (Table 1), ONCT-534 should not be taken by the subject at home, but rather will be administered in the clinic.

#### **6.2.2. Dose Modification of ONCT-534**

The daily dose of ONCT-534 should be held and/or adjusted as outlined in Table 2.

**Table 2: Dose Modification of ONCT-534**

Toxicity	Treatment Modification
Grade 3 hematological toxicity	Hold treatment until recovery to Grade 1 or baseline; resume treatment at one level lower a . Transfusion and growth factors are allowed. Discontinue treatment if not resolved in 21 days.
Grade 4 or recurrent Grade 3 hematological toxicity	Hold treatment until recovery to Grade 1 or baseline; resume treatment at 2 dose levels lower a . Transfusion and growth factors are allowed. Discontinue treatment if not resolved in 21 days.
Grade 3 non-hematologic toxicity	Hold treatment until recovery to Grade 1 or baseline; resume treatment at one dose level lower a . Discontinue treatment if not resolved within 21 days.
Grade 4 non-hematologic toxicity	Permanently discontinue treatment.

a If the subject is receiving ONCT-534 at 40 mg/day, then reduce to 20 mg/day. If the subject is receiving ONCT-534 at 20 mg/day then discontinue treatment.

No dose modifications are required for the following:

- Grade 3 nausea/vomiting, anorexia, constipation, or diarrhea lasting for < 72 hours with optimal supportive care;
- Grade 3 fever lasting < 48 hours;
- Grade 3 blood urea nitrogen (BUN) or electrolyte abnormality that lasts up to 72 hours, is not considered clinically significant, and resolves spontaneously or responds to conventional medical interventions;
- Grade 3+ amylase or lipase that is not associated with symptoms or clinical manifestations of pancreatitis;
- Grade 3 fatigue, asthenia, or alopecia.

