Study Design ONCT-534 (previously known as GTx-534 or UT-34) is a dual-action androgen receptor inhibitor (DAARI) with a novel mechanism of action that includes inhibition of androgen receptor (AR) function and degradation of the AR protein mediated by interaction with the N-terminal domain (NTD) of the AR. ONCT-534 has demonstrated preclinical activity in prostate cancer models against both unmutated AR, and against multiple forms of AR alteration, including those with AR amplification, mutations in the AR ligand binding domain (LBD), and splice variants with loss of the AR LBD. Study ONCT-534-101 is a Phase 1/2, multi-center study to evaluate the safety, tolerability, antitumor activity, and pharmacokinetics (PK) of ONCT-534 in subjects with R/R histologically confirmed mCRPC who have relapsed or are refractory to at least one next-generation ARSI, such as enzalutamide, darolutamide, apalutamide, or abiraterone. The study will be separated into Phase 1 Dose Escalation and Phase 2 Dose Expansion portions. In all parts of the study, after a Screening period, eligible subjects with mCRPC will be enrolled to receive their assigned dose regimen of ONCT-534. ONCT-534 will be administered orally daily for 2 years or until documented progressive disease and no longer clinically benefiting from treatment, development of unacceptable toxicity, withdrawal of consent, end of study, or other discontinuation or withdrawal reasons, whichever occurs first (see Section 7.1 for details). Phase 1 Dose Escalation The Phase 1 portion of the study will use an adaptive Bayesian Optimal Interval (BOIN) Design (Liu and Yuan, 2014; Yuan et al., 2016). The anticipated number of subjects in the Phase 1 portion is approximately 27, in the expected 5 dose cohorts. The primary objectives are to assess the safety, tolerability, and dose-limiting toxicity (DLT) of ONCT-534 at escalating doses and to determine the MTD of ONCT-534 to inform the 2 dose levels or schedules to be tested in Phase 2. DLT will be assessed during the first 28 days of study treatment.	

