## **7. STUDY DISCONTINUATION AND PARTICIPANT DISCONTINUATION/WITHDRAWAL**

### **7.1. Reasons for Subject Removal from the Study**

Reasons for subject discontinuation from the study may include the following:

- Progressive disease and no longer clinically benefiting from treatment.
- Development of unacceptable toxicity.
- Withdrawal of consent.
- Loss to follow-up.
- Study termination by the Sponsor.
- Death.

PCWG3 ([Scher et al., 2016](#)) introduces the concept of no longer clinically benefiting to underscore the distinction between first evidence of progression and the clinical need to

terminate or change treatment, and the importance of documenting progression in existing lesions as distinct from the development of new lesions.

Treatment beyond preliminary evidence of progression (e.g., unconfirmed progressive disease according to PCWG3) or radiologic progression for measurable disease according to RECIST v1.1 is permitted for subjects who may derive benefit from continued study participation (in the opinion of the Investigator and in consultation with the Sponsor), provided the subject is clinically stable, and is able to continue treatment until the next imaging assessment. One example of preliminary evidence of progression is the appearance of new abnormalities on the first bone scan after starting ONCT-534 treatment.

To continue treatment beyond preliminary evidence of progression, the following criteria must be met:

- Absence of signs and symptoms indicating clinically significant progression of disease.
- No decline in ECOG or Karnofsky performance status ([Appendix 1](#)).
- Absence of symptomatic rapid disease progression requiring urgent medical intervention (e.g., symptomatic pleural effusion, spinal cord compression).
- Reconsent using a written informed consent document that details all Regulatory Authority-approved therapy, and potential clinical benefit, that the subject may be foregoing to continue receiving the investigational product.

An End of Treatment visit should be conducted for subjects who discontinue prior to the Week 108 visit as indicated in the Schedule of Assessments (see Section 1.3). Subjects will be contacted for a safety assessment 30 days (+7 days) after the last dose of ONCT-534 for all subjects who discontinue treatment (either at Week 108 or Early Termination).

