### 8.3.7. Definition of Dose-Limiting Toxicity

DLT will be defined as any of the following attributed to ONCT-534 treatment occurring in the first 28 days of ONCT-534 treatment:

1. Any death not clearly related to the underlying disease or extraneous causes (e.g., accident or trauma).
2. Dose delays due to an AE lasting more than 14 days.
3. Non-hematologic toxicity:
  - a. Grade 3 or higher.
  - b. Hy’s law cases ([Appendix 1](#)).
  - c. AST or ALT  $> 8 \times$  ULN.
  - d. AST or ALT  $> 5 \times$  ULN lasting more than 14 days.
4. Hematologic toxicity
  - a. Grade 4 neutropenia or thrombocytopenia lasting more than 7 days.
  - b. Grade 3 or higher thrombocytopenia with clinically significant bleeding.
  - c. Neutropenic fever.

The definition of DLT will exclude:

- Grade 3 nausea/vomiting or diarrhea for less than 72 hours with adequate antiemetic and other supportive care.
- Grade 3 fatigue for less than 1 week.
- Grade 3 or higher BUN or electrolyte abnormality that lasts up to 72 hours, is not clinically complicated, and resolves spontaneously or responds to conventional medical interventions.
- Grade 3 or higher amylase or lipase that is not associated with symptoms or clinical manifestations of pancreatitis.

During the DLT evaluation period (Day 1 through Day 28 of study treatment) of the dose escalation cohorts, AEs identified as DLTs are required to be reported by the Investigator to the Sponsor immediately (no more than 24 hours after learning of the event), who will notify the SRC. Refer to Section 8.3.9 and Section 8.4 for recording and reporting procedures.

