**Table 10: Hy's Law**

1	ALT or AST $\geq$ 3 times ULN
2	Total bilirubin > 2 times ULN, without elevated serum alkaline phosphatase
3	No alternate explanation, such as viral hepatitis A, B, or C; pre-existing or acute liver disease; or another drug capable of causing the observed injury

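### Table 2 has no Hy's law rule: a Grade 3 case that recovers within 21 days is directed back onto ONCT-534 one level lower, and a case below Grade 3 has no required hold

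*Combined protocol and SAP*

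**What the plan says.** Section 6.2.2 makes one table the governing rule: "The daily dose of ONCT-534 should be held and/or adjusted as outlined in Table 2". Table 2 has four rows:

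- Grade 3 hematological: hold, then restart one level lower.
- "Grade 4 or recurrent Grade 3 hematological toxicity": hold, then restart two levels lower.
- Grade 3 non-hematologic: "Hold treatment until recovery to Grade 1 or baseline; resume treatment at one dose level lower"; discontinue if not resolved within 21 days.
- Grade 4 non-hematologic: permanent discontinuation.

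Footnote a takes a subject from 40 to 20 mg/day and then ends treatment: "If the subject is receiving ONCT-534 at 20 mg/day then discontinue treatment". The list below the table of events needing no modification contains no liver item.

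Hy's law appears in two other places. Section 8.3.7 lists it as item 3b of the dose-limiting toxicity (DLT) definition, apart from item 3a (Grade 3 or higher), for events "attributed to ONCT-534 treatment occurring in the first 28 days of ONCT-534 treatment". Table 10 in Appendix 1 defines it as ALT or AST at least 3 times ULN, "Total bilirubin > 2 times ULN" without raised alkaline phosphatase, and no other explanation. The definition uses ULN multiples, not grades.

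The general ground for stopping appears in the Synopsis ("development of unacceptable toxicity, withdrawal of consent, end of study") and in Section 7.1 ("Development of unacceptable toxicity"). Neither place defines it.

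**The concern.** The protocol recognises Hy's law as a distinct event and, through Table 10 and the attribution clause in Section 8.3.7, as liver injury ascribed to the drug with nothing else to account for it. The dosing table then treats it like any other toxicity of the same grade. At Grade 3 with timely recovery, following the table means giving the drug again. Below Grade 3, the table says nothing.

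This matters because ONCT-534 has not been given to humans before, and Section 2.4.3 cites potential liver effects as a reason for close monitoring without attaching a dosing action. The stake is the safety of the individual subject, since such an event may be rare but its harm may be irreversible. The dose-finding statistics are not at issue.

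**Working it through.** The plan states no figure to reproduce. The check applies Table 2 to a Hy's law case and then looks for any other text that would require a hold or stop.

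**Step 1. Table 2 applied by grade**

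| Hy's law case | What Table 2 requires |
|---|---|
| Grade 4 | Permanent discontinuation |
| Grade 3, not resolved within 21 days | Discontinuation |
| Grade 3, recovered within 21 days, dose 40 mg/day or more | Restart one level lower |
| Grade 3, subject at 20 mg/day | Discontinuation |
| Below Grade 3 | No row applies, so no required hold |

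The last line is conditional. The protocol does not print the CTCAE laboratory cut-offs, so it cannot be shown from the documents alone that a case meeting Table 10 can fall below Grade 3. The separate listing of items 3a and 3b suggests it but does not prove it.

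**Step 2. Size of the dose reduction at restart**

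Inputs: initial dose levels 40, 80, 160, 300 and 600 mg (Section 4.1.1), and the 20 mg step (Table 2, footnote a). Ratio = restart dose / previous dose.

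- 600 to 300 mg: 300/600 = 0.50
- 300 to 160 mg: 160/300 = 0.53
- 160 to 80 mg: 80/160 = 0.50
- 80 to 40 mg: 40/80 = 0.50
- 40 to 20 mg: 20/40 = 0.50

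**Step 3. Repeat events**

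The recurrence row covers hematological toxicity only, so the Grade 3 non-hematologic row can be applied again at each lower level until 20 mg. The number of restarts the text allows equals the number of steps down to 20 mg: 1 from 40 mg, 2 from 80, 3 from 160, 4 from 300 and 5 from 600. This is an upper bound on the wording, not a forecast.

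**Step 4. Does any other text require a hold or stop for the affected subject?**

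- Section 8.3.7 and Section 8.4: 24-hour reporting of a DLT and notice to the Safety Review Committee (SRC). No action on the subject's own dose.
- Section 7.4: the toxicity trigger for a study halt needs a related Grade 4 event that is both unmanageable and unexpected. The other triggers are death and new malignancy.
- Section 8.3.2: an abnormality that leads to interruption must be recorded. It does not say when to interrupt.
- Section 8.5: additional tests and follow-up, no dosing rule.
- Synopsis and Section 7.1: unacceptable toxicity, undefined.

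None sets a hold or stop for a Hy's law case.

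**Step 5. How long the DLT listing applies**

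Item 3b covers 28 days. Maximum treatment is 108 x 7 = 756 days, and 28/756 = 3.7%. For an assumed 24-week course, 24 x 7 = 168 days and 28/168 = 16.7%. After that window, and in Phase 2, only the generic Table 2 rows and ordinary adverse event handling remain. These percentages describe the DLT definition; the restart rule applies throughout treatment.

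**The case against.** The strongest reply is that a grade-based scheme is coherent and that judgement fills the gap. Section 6.2.2 says the dose should, not must, follow Table 2. Unacceptable toxicity ends treatment. DLT item 2 contemplates dose delays for an adverse event with no grade threshold. An investigator who has concluded that no other cause exists can also stop the drug. In the first 28 days the sponsor hears within 24 hours and the SRC is told; Section 8.3.6 asks that important medical events usually be treated as serious, which brings 24-hour reporting in both phases; and chemistry is scheduled at Day 14 and Weeks 4, 6, 8 and 12, then onward. An unnoticed restart would therefore be unusual, at least early on. This stands, and it limits the expected harm. It does not close the gap: none of these provisions requires a hold or stop, and the one rule that speaks to the subject's dose points towards restart.

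The evidence for cases below Grade 3 is thin. Items 3c and 3d, the AST/ALT thresholds, are also listed apart from item 3a, so the list may simply overlap. That part must stay conditional. The Grade 3 restart does not depend on it.

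Five restarts from 600 mg would need five successive Grade 3 events, each recovering in time, with nobody stopping treatment. The missing recurrence limit also affects all non-hematologic toxicity, not only liver injury. Both points are fair.

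The animal signal is modest: Section 2.4.1 calls the liver and kidney findings non-adverse. It also names the liver as a target organ and excepts oval cell hyperplasia in dogs from full reversibility, so a cautious rule remains reasonable.

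**Conclusion.** The concern holds and should be fixed. None of the four rows in Table 2 is specific to Hy's law, AST/ALT or bilirubin. A Grade 3 case that recovers within 21 days is directed to restart at 50% to 53% of the previous dose, unless the subject is already at 20 mg/day. The ratios assume the initial dose ladder; the SRC may add levels or schedules. Any case below Grade 3 is left to undefined judgement, on the inference that such cases exist.

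What is missing is a mandatory rule; the protocol does not forbid stopping. The documents give no basis for estimating how many subjects would be affected. BOIN decisions, error rates and sample size do not change.

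**What to change.** Add one row to Table 2, for both phases and the whole treatment period, that overrides the Grade 3 non-hematologic row:

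- When the Table 10 laboratory limits are met, hold ONCT-534 at once and start a work-up.
- If the case is confirmed with no other explanation, discontinue permanently. The row should say what counts as confirmed.
- If another cause is found, the clinical team decides on restart and on the interval for repeat tests.

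Gilbert's syndrome belongs under the third point, because inclusion criterion 13f admits those subjects with bilirubin up to 2.5 times ULN, already above the Table 10 bilirubin limit of 2. The row would not trigger at entry, since criterion 13e caps AST/ALT at 2.5 times ULN, below the Table 10 limit of 3. The Grade 4 row stays as it is.

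The cost is one row in the next amendment, with no added subjects or scheduled visits. The downside is an occasional subject who stops treatment and some unscheduled liver tests, which Section 8.1.5 already permits when clinically indicated.

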### **6.2.3. Light Protective Measures**

ONCT-534 has been shown to absorb light in the 290 to 700 nm range (i.e., the range of natural sunlight). Therefore, study subjects should avoid extensive sun exposure and protect themselves (e.g., long sleeves, hat, sunscreen) and avoid phototherapy and tanning salons while taking ONCT-534 and for 1 month thereafter.

### **6.3. Concomitant Therapy or Procedures**

Therapy for concomitant medical conditions or for symptom management may be given if clinically indicated at the discretion of the Investigator. Concomitant therapy consists of any medication (e.g., prescription drugs, over the counter drugs, vaccines, herbal or homeopathic

remedies, nutritional supplements) used by a subject in addition to protocol-mandated treatment from the first dose of ONCT-534 until going off study. All such medications should be reported and recorded in the electronic Case Report Form (eCRF).

The Investigator's decision to authorize the use of any drug, other than study treatment, will take into consideration the safety of the subject, the medical need, the potential for drug-drug interactions, the possibility of masking symptoms of a more significant underlying event, and whether the use of the drug will compromise the outcome or integrity of the study.

### **6.3.1. Permitted Concomitant Therapies**

Subjects may receive the following therapies during the study:

- Treatment for any unrelated medical condition(s);
- Supportive care including but not limited to antibiotics, analgesics, growth factors, and transfusions;
- Supportive non-cancer directed therapies such as bisphosphonates or denosumab;
- Palliative radiation: subjects may receive limited palliative radiation therapy at any time and with schedules at the discretion of the Investigator provided that the schedule does not interfere with protocol-specific assessments. Lesions included in a radiotherapy field may not be used for disease assessments, and appropriate documentation of radiated lesions must be captured in the eCRF.

### **6.3.2. Prohibited Medications**

No systemic anti-cancer therapies (including chemotherapy, antibody therapy, immunotherapy, cellular therapy, or other experimental therapies) for the subject's cancer are permitted while the subject is on this study, other than ongoing LHRH agonists.

Subjects are not allowed to participate concurrently in any other therapeutic clinical study.

Caution should be exercised when ONCT-534 is co-administered with a strong inducer or inhibitor of CYP3A4, or a substrate of CYP3A4 with a narrow therapeutic index, or a substrate of CYP2C9 or CYP2C19 with a narrow therapeutic index ([Appendix 3](#)), and an alternate medication should be considered.

Grapefruit, Seville oranges or their juice, and concomitant medications that are CYP3A4 substrates should be taken either 2 hours prior or 8 hours after ONCT-534 administration.

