## 5.2. Subject Exclusion Criteria

A subject will be excluded from entering the study if any of the following criteria apply:

1. Subject has small cell prostate cancer or neuroendocrine disease histology, including mixed histology.
2. Subject has metastases to the brain or CNS.
3. Subject is receiving concurrent systemic anti-cancer therapies (including chemotherapy, antibody therapy, immunotherapy, cellular therapy, or other experimental therapies) except for ongoing androgen inhibiting therapy such as LHRH agonists. Supportive non-cancer directed therapies such as bisphosphonates or denosumab are allowed.
4. Subjects taking a strong inducer or inhibitor of CYP3A4 ([Appendix 3](#)), or a substrate of CYP3A4, CYP2C9 or CYP2C19 with a narrow therapeutic index ([Appendix 3](#)) are excluded unless the Investigator considers the medication essential with no alternatives available.
5. Subject had major surgery within 30 days prior to start of study drug.
6. Subject has current, untreated pathologic long-bone fractures(s), or risk of imminent pathologic fracture(s).
7. Subject has current or imminent spinal cord compression.
8. Subject has an active seizure disorder or a history of seizure disorder(s).
9. Subject has evidence of active human immunodeficiency virus (HIV), hepatitis B virus (HBV), or hepatitis C virus (HCV) infection. For further definition see Section [8.1.1.5](#).
10. Subject has any other serious illness or medical condition that would interfere with study participation, such as but not limited to:
  - a. Clinically significant, active cardiovascular disease: myocardial infarction or coronary artery bypass grafting within 6 months, unstable angina, congestive heart failure of New York Heart Association Classification Class III or IV ([Appendix 1](#)), or serious cardiac arrhythmia requiring medication.
  - b. Pulmonary disease requiring supplemental oxygen.
  - c. A known gastrointestinal condition that would limit the ingestion or gastrointestinal absorption of drugs administered orally.
11. Subject has abnormal ECGs that are clinically significant, including average QTcF > 450 ms, or a history of Torsade de Pointes.
12. Subject has any infection requiring parenteral antibiotic therapy or causing fever (temperature > 100.5°F or 38.1°C) within 1 week prior to first dose.

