## 7.2. Subject Replacement

The BOIN design does not require that subjects in the Phase 1 portion of the study who are not DLT evaluable (as defined in Section 9.2) be replaced unless the cohort size is one. Subjects who receive ONCT-534 and withdraw prior to Day 28 due to a DLT will not be replaced, and subjects who are not evaluable may be replaced at the discretion of the Sponsor and SRC.

Subjects in the Phase 2 portion of the study may be replaced, after discussing with the Sponsor, if they are not evaluable for efficacy (as defined in Section 9.2) for the purpose of estimating clinical activity of ONCT-534 and discontinued the study for reasons not related to study drug or disease progression.

Additional subjects may be enrolled beyond the planned sample size to provide sufficient data for analysis of safety, efficacy, PK and/or pharmacodynamics.

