## **9.2. Populations for Analysis**

The DLT-evaluable Population is defined as all subjects in the Phase 1 Dose Escalation part of the study who receive ONCT-534 and either complete the 28-day DLT observation period or discontinue the study early due to a DLT. Subjects will be grouped by the dose received.

The Safety Population is defined as all subjects who receive at least one dose of ONCT-534. Subjects will be grouped by the ONCT-534 dose received at study entry.

The Efficacy-evaluable Population is defined as all subjects who receive ONCT-534 and complete at least one post-treatment disease assessment and do not discontinue due to clinical evidence of disease progression without documentation prior to obtaining post-treatment disease assessment. Subjects will be grouped by dose received.

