### APPENDIX 3. CYTOCHROME P-450 INHIBITORS, INDUCERS AND SUBSTRATES

**Table 16: Cytochrome P-450 Inhibitors, Inducers and Substrates**

CYP3A4 Substrates with a Narrow Therapeutic Index
 
Acenocoumarol, aminophylline, amiodarone, amitriptyline, argatroban, astemizole, baricitinib, cabergoline, carbamazepine, clomipramine, clonidine, conivaptan, cyclosporine, digitoxin, dihydroergotamine, dofetilide, dronedarone, ergotamine, fosphenytoin, imipramine, levacetylmethadol, lomitapide, mycophenolic acid, nortriptyline, phenprocoumon, phenytoin, pimozide, quinidine, ruxolitinib, siponimod, sirolimus, tacrolimus, theophylline, tianeptine, tolvaptan, warfarin
 
Source: https://go.drugbank.com/categories/DBCAT004028. A complete list of CYP3A4 substrates may be found at https://go.drugbank.com/categories/DBCAT002646

Strong CYP3A4 Inhibitors
 
Amiodarone, amprenavir, atazanavir, boceprevir, clarithromycin, cobicistat, conivaptan, curcumin, danazol, danoprevir, darunavir, delavirdine, diltiazem, ditiocarb, econazole, efavirenz, elvitegravir, ergotamine, indinavir, itraconazole, ketoconazole, levoketoconazole, lonafarnib, loperamide, lopinavir, methimazole, midostaurin, naloxone, nefazodone, nelfinavir, posaconazole, ritonavir, saquinavir, stiripentol, telaprevir, telithromycin, terfenadine, tipranavir, troleandomycin, voriconazole
 
Source: https://go.drugbank.com/categories/DBCAT002647

Strong CYP3A4 Inducers
 
Carbamazepine, dexamethasone, fosphenytoin, lumacaftor, mitotane, pentobarbital, phenobarbital, phenytoin, primidone, rifampicin, rifamycin, rifapentine, rifaximin, rimexolone, St. John's Wort, Carbamazepine, ivosidenib, lumacaftor, mitotane, phenytoin, rifampin, St. John's wort
 
Source: https://go.drugbank.com/categories/DBCAT002649

CYP2C9 Substrates with a Narrow Therapeutic Index
 
Acenocoumarol, amitriptyline, dicoumarol, enasidenib, fluindione, fosphenytoin, phenobarbital, phenprocoumon, phenytoin, quinidine, ruxolitinib, Siponimod, trimipramine, valproic acid, warfarin
 
Source: https://go.drugbank.com/categories/DBCAT004033

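### Strong CYP3A4 inducers and inhibitors face a weaker rule on study (6.3.2) than at entry (Exclusion 4), even in the 28-day DLT window; a small wording change would align them

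*Combined protocol and SAP*

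**What the plan says.** **At entry.** Section 5.2, criterion 4, covers subjects taking a strong CYP3A4 inducer or inhibitor from Appendix 3. They "are excluded unless the Investigator considers the medication essential with no alternatives available".

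**On study.** Section 6.3.2 is headed as a list of prohibited medications, but for the same drugs it reads "Caution should be exercised when ONCT-534 is co-administered with a strong inducer or inhibitor of CYP3A4" and adds that a substitute should be considered. The section gives hour-based separation rules for grapefruit and for ordinary CYP3A4 substrates, but none for strong inducers or inhibitors. It has no separate rule for the DLT window.

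**What counts as co-medication.** Section 6.3 states "Concomitant therapy consists of any medication (e.g., prescription drugs, over the counter drugs, vaccines, herbal or homeopathic" remedies and supplements. Table 16 in Appendix 3 has "rifapentine, rifaximin, rimexolone, St. John's Wort, Carbamazepine, ivosidenib" among the strong inducers and "boceprevir, clarithromycin, cobicistat, conivaptan, curcumin, danazol, danoprevir" among the strong inhibitors, so both lists contain products available without prescription. They also contain supportive-care drugs: dexamethasone (inducer) and loperamide (inhibitor).

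**Who enters the DLT count.** Section 9.2 takes Phase 1 subjects "who receive ONCT-534 and either complete the 28-day DLT observation period or discontinue the study early due to a DLT", grouped by dose received, with no condition on co-medication.

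**The concern.** Section 2.2.2 reports that CYP3A4 is the main route of metabolism in vitro. A subject who takes a strong inducer through most of the window may therefore have lower exposure than the nominal dose implies. If that subject has no DLT, the result still counts in full toward escalation. With a strong inhibitor the reverse holds: a DLT at raised exposure is charged to the nominal dose, and the subject carries avoidable risk in a first-in-human study.

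A subject who could not enter on such a drug may start it just after Day 0 under a weaker test. At the first two dose levels one subject can be the whole cohort, provided that no DLT, no worsening from Grade 2 to Grade 3 and no new Grade 2 AE occurs. The issue is sustained use. A short antiemetic or antidiarrheal course is unlikely to matter much.

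**Working it through.** **1. Comparison of the text.** The drugs and the appendix are the same in both places. The entry rule is an exclusion with a narrow exception; the on-study rule is advice. Sections 6.3, 6.3.1, 8.3.7, 9.2 and 9.5.1 contain no stricter on-study rule and none specific to Days 0 to 28.

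**2. The plan's own decision rule.** The plan gives no figure for this point, so I checked the rule used in the illustration. The target is φ = 0.30 (Section 9.5.1). I assumed the usual BOIN defaults φ1 = 0.6φ = 0.18 and φ2 = 1.4φ = 0.42, which the protocol does not state.

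- Escalation boundary: ln(0.82/0.70) / ln[(0.30×0.82)/(0.18×0.70)] = 0.2365 (plan: 0.236).
- De-escalation boundary: ln(0.70/0.58) / ln[(0.42×0.70)/(0.30×0.58)] = 0.3585 (plan: 0.359).

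The counts in Table 5 reproduce too. The dose-finding rule itself is not in question.

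**3. Illustration, given one affected subject.** These rates are assumptions: DLT risk 0.30 at the current dose, and 0.15 for one subject whose exposure is halved. Halving is about one dose level, since the steps are 80/40 = 2, 160/80 = 2, 300/160 = 1.875 and 600/300 = 2, with dose-proportional exposure also assumed. Table 5 limits: with 3 subjects, escalate at 0 DLTs and de-escalate at 2 or more; with 6, escalate at 1 or fewer and de-escalate at 3 or more.

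| | Nobody affected | One subject on a strong inducer |
|---|---|---|
| 3 subjects, escalate | 0.7³ = 0.343 | 0.85×0.49 = 0.417 |
| 3 subjects, de-escalate | 0.216 | 0.85×0.09 + 0.15×0.51 = 0.153 |
| 6 subjects, escalate | 0.420 | 0.85×0.528 + 0.15×0.168 = 0.474 |
| 6 subjects, de-escalate | 0.256 | 0.209 |

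- If the affected subject's risk is 0.10 to 0.25, escalation with 3 subjects is 0.90×0.49 = 0.441 down to 0.75×0.49 = 0.368.
- Cohort of one, ignoring the Grade 2 trigger: 0.70 becomes 0.85. If the rates are 10% and 5%, 0.90 becomes 0.95.
- Strong inhibitor raising one subject's risk to 0.50 (range 0.40 to 0.60): the chance of 0 DLTs in 3 falls from 0.343 to 0.49×0.50 = 0.245 (0.294 to 0.196).

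**4. Allowing for how rarely it may happen.** Suppose each subject independently has probability f of sustained inducer use. Average risk is then 0.30 − 0.15f, and the chance of 0 DLTs in 3 is (0.70 + 0.15f)³.

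- f = 0.02: 0.703³ = 0.347
- f = 0.05: 0.7075³ = 0.354
- f = 0.10: 0.715³ = 0.366

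Against 0.343 these are shifts of about 0.4 to 2.3 percentage points. The values of f are assumptions too.

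**5. Would removing the affected subject from the DLT count help?** Same rates, 3 subjects, removing him only if DLT-free:

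- Not replaced (2 remain; de-escalate at 1 or more): escalate 0.85×0.49 = 0.417; de-escalate 0.85×0.51 + 0.15×0.51 = 0.510.
- Replaced: escalate 0.85×0.343 = 0.292; de-escalate 0.85×0.216 + 0.15×0.51 = 0.260.

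Without replacement, escalation is as likely as when he is counted, and de-escalation more than doubles from 0.216. With replacement, an error of about +7 points in escalation becomes one of about −5.

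**The case against.** The strongest reply is that the plan already has several layers of protection.

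- Section 6.3 obliges the investigator to weigh medical need, interaction potential and any harm to the integrity of the study.
- Section 8.1.1.3 records over-the-counter, herbal and supplement use at Screening. A candidate already on St. John's wort or curcumin would meet Exclusion 4 and would hardly qualify for the exception.
- Section 8.1.9 samples PK on Days 0, 1, 14 and 15 and at Week 4, so marked under-exposure could be seen.
- Sections 4.1.1 and 10.1.4 give the SRC the PK data and the dose decision. Section 9.5.1 makes BOIN a guide for that decision, so the percentages above are mechanical and not the trial's actual probabilities.

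A stricter test at entry is also understandable: a candidate can be turned away, but an enrolled patient's medical need cannot.

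Most of this stands and limits the point. What remains is that these safeguards are advisory or act after the fact. None carries the entry test into the window, and none requires that such use be put before the SRC. The protocol refers to an SRC Charter and a SAP for detail. They may say more, but no text from either is in the document reviewed.

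A reader might also infer that an affected subject should lose DLT-evaluable status. The arithmetic does not favor this. Such a rule would make evaluability depend on outcome. It would also need compulsory replacement, whereas Section 7.2 says that BOIN does not require that Phase 1 subjects "who are not DLT evaluable (as defined in Section 9.2) be replaced unless the cohort size is one", and otherwise "subjects who are not evaluable may be replaced at the discretion of the Sponsor and SRC".

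**Conclusion.** The inconsistency holds on the text: the same drugs meet a firm test at entry and only advice afterwards, including in the period that determines the DLT count. The effect on dose finding is probably small, and its size cannot be derived from the documents. They give no interaction magnitude, no human PK and no expected frequency of use. Section 2.2.2 also reports glucuronidation and sulfatase pathways, so the in vivo share of CYP3A4 is unknown. Every percentage above is an illustration on assumed rates; those in step 3 are conditional on one affected subject being in the cohort.

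Two stronger readings are not supported. One is that the gap undermines the MTD: the boundaries are sound, and the SRC sees PK before it moves the dose. The other is that tightening 6.3.2 would remove the problem entirely: a subject on an essential inducer or inhibitor could still enter, or start the drug, under the same exception. This is a low-priority, cheap improvement, worth making mainly for subject safety and for a cleaner link between dose and exposure.

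**What to change.** In Section 6.3.2, state that from Day 0 through Day 28 of Phase 1 the strong CYP3A4 inducers and inhibitors in Appendix 3 are not permitted unless they meet the Exclusion 4 test. Allow brief supportive-care courses, for example of dexamethasone or loperamide, up to a duration that the sponsor sets. Require that any such use in the window be flagged to the SRC, with that subject's PK, before the dose decision.

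Leave Sections 9.2 and 7.2 unchanged.

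The cost is a few sentences of protocol text and one flag to the SRC; Section 6.3 already has concomitant medications recorded in the eCRF. The downside is a small restriction on supportive care for 28 days, eased by the brief-course allowance. Essential-drug exceptions remain and are left to SRC review.
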